### **Contact between or after study visits**

Participants will be offered phone access to the intervention facilitator between or after study visits if they develop new or intervening concerns. The intervention facilitator will offer to connect participants with available resources and answer targeted questions but will not engage in formal psychotherapeutic counseling during these contacts. The number and reason for participants' contact with the intervention facilitator will be logged and evaluated at the end of the study.

### **Contact with bereaved participants**

Patient participants in this study will all have a diagnosis of metastatic breast cancer and are therefore at risk of dying from their underlying disease during the study period. If a participant who is a breast cancer patient dies during the study period or up to six months following their participation in the study, the intervention facilitator will call the bereaved co-parent two weeks following the death of the patient (or within two weeks of the study team's notification of the death) to offer condolences and to provide brief psychosocial support to the participant. The intervention facilitator will follow a semi-structured telephone script that is included in the attachments.

### **Participant self-report study measures**

Participants will complete several outcome measures. Each participant in the dyad will complete the study measures separately. Participants may complete some or all of the surveys and they can skip any questions they find distressing.

The measuring instruments, schedule of administration, and estimated duration are listed in Table 1 and include the following: Demographic and social history questions, the

Eastern Cooperative Oncology Group Performance status scale (modified for self-report), Parenting Concerns Questionnaire-Revised (PCQ-R), the Hospital Anxiety and Depression Scale (HADS), the Functional Assessment of Cancer Therapy – Palliative Care, FACIT-Pal, the Couples Illness Communication Scale (CICS) and several investigator-designed parental preparedness questions (see Appendix C for measures).

**Table 1. Measuring instruments**

Domain	Measure	Time (min)	Participant	Schedule
Demographic and baseline history forms	Demographic form Baseline history form	5	Patient Co-parent	Baseline
Acceptability	Study Visit Assessment form	5	Patient Co-parent	Visit 1 Visit 2 Visit 3 (if applicable)
Depression and anxiety	Hospital Anxiety and Depression Scale (HADS)	5	Patient Co-parent	Baseline Visit 1 Visit 2 Visit 3 (if applicable)
Parenting Concerns	Parenting Concerns Questionnaire-Revised (PCQ-R)	5	Patient Co-parent	Baseline Visit 1 Visit 2 Visit 3 (if applicable)
Parenting preparedness	Co-parenting and communication form	5	Patient Co-parent	Baseline Visit 1 Visit 2 Visit 3 (if applicable)
Health-related Quality of Life	Functional Assessment of Chronic Illness Therapy-Palliative Care (FACIT-Pal)	7	Patient	Baseline Visit 1 Visit 2 Visit 3 (if applicable)
Communication	Couples Illness Communication Scale (CICS)	2	Patient Co-parent	Baseline Visit 1 Visit 2 Visit 3 (if applicable)
Performance status	Eastern Cooperative Oncology Group Performance Status Scale (ECOG)	2	Patient	Baseline Visit 1 Visit 2 Visit 3 (if applicable)

### Study team assessments

After each study visit, the PI and intervention facilitator will independently complete an intervention fidelity checklist.

### Measures

#### **Hospital Anxiety and Depression Scale (HADS)**

The HADS is a 14-item self-administered rating scale to assess depression and anxiety symptoms in patients with physical illness (see Appendix D). The HADS has two 7-item sub-scales addressing depression and anxiety. It is graded on a 4-point scale with scores ranging from 0 to 42 (or 0-21 for each subscale) with higher scores representing greater

degrees of mood symptoms. The HADS is a well-validated instrument frequently used in oncology populations. The average time to complete the HADS is 3-5 minutes.

### **Couples Illness Communication Scale (CICS)**

The CICS is a brief self-report measure of illness-related couple communication. The CICS consists of 4 items measured on a 5-point Likert-type scale. It has demonstrated good acceptability, internal consistency, construct and convergent validity among couples in which one partner has cancer. The average time to complete the CICS is 1-2 minutes.

### **Eastern Cooperative Oncology Group Performance Status Scale (ECOG)**

The ECOG evaluates the severity of symptoms and amount of assistance the participant requires to complete “normal activities” using a 5-point scale. The ECOG is used to assess how the disease affects the daily living abilities of the patient and determine appropriate treatment and prognosis. It has been modified for patient self-report and takes 1 minute to complete.

### **Parenting Concerns Questionnaire-Revised (PCQ-R)**

The PCQ-R is a 21-item self-administered assessment of parenting concerns in advanced cancer patients. The PCQ-R is a modified version of the original Parenting Concerns Questionnaire – a general assessment of parenting concerns in cancer patients – with question items specifically addressing concerns of advanced cancer patients. The PCQ-R is measured on a 4-point scale and total score range for the PCQ is 0-63 with higher scores indicating greater distress. The original PCQ has demonstrated good internal consistency and face validity. The average time to complete the PCQ-R is 5 minutes.

### **Functional Assessment of Cancer Illness Therapy – Palliative Care (FACIT-Pal)**

The FACIT-Pal is a 46-item self-administered assessment of general HRQOL in cancer patients. It has been validated in the literature and permits measurement of a number of symptoms including nausea, pain, and insomnia. It is graded on a five-point scale and has four sub-scales addressing emotional, social/family, physical and functional well-being. The average time to complete the FACIT-Pal is 5-7 minutes.

### **Investigator-designed questions**

Investigator-designed questions include items that are not found in validated scales or individual items from validated scales (to reduce participant response burden). Items on this form include questions about prior communication with children about illness, perceived social support, illness beliefs, and co-parenting support. The estimated time to complete these items is 5-7 minutes.

### **Satisfaction assessment**

The Lyon Satisfaction questionnaire is a validated 13-item assessment of acceptability and perceptions of visits in this population. One additional investigator-designed item asks participants to designate their overall satisfaction with their visit on a 5-point Likert-type scale. The estimated time to complete these items is 3-5 minutes.

### **Post-intervention study interview**

Following completion of study visits with the intervention facilitator, participants will individually participate in a semi-structured interview with a member of the study team (PI or RA) to obtain feedback on the intervention (see Appendix F). If participants elect to withdraw from the study prior to completion of the scheduled intervention study visits, they will remain eligible to participate in this interview. The post-intervention interview will occur face-to-face in a private room of NCCH or via telephone and each member of the dyad will participate separately. The interview is expected to take 30-45 minutes. Participants are not required to answer questions they find emotionally distressing. All interviews will be audiotaped and then professionally transcribed. Interview audiofiles and transcriptions will be stored in a password-protected file within an electronic firewall-secured server maintained by the UNC School of Medicine.

Optional 6-month follow-up interview

If a participant is willing, the study team will follow up with them 6 months after finishing the study sessions. These participants will be asked to participate in an additional interview individually (separate from their partner). The interview is expected to take 20-30 minutes, and can be done in person or over the phone. This interview will also be audiotaped and transcribed. Participation in the 6-month follow-up interview is completely optional.

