### **Study visits**

During the study visits, the patient and co-parent participate together as a dyad with the intervention facilitator. The standard intervention will include Study Visits 1 and 2. Study Visit 3 is optional and will be offered to participant dyads who wish to have a third session with the intervention facilitator. Study visits will consist of two parts: (1) a face-to-face meeting with the intervention facilitator, and (2) data collection with the research assistant.

We will schedule study visits at the convenience of the participants. The participants will be provided with a choice regarding study visit location. The study visits will be conducted in either: (1) a clinical patient care area of the NCCH, (2) the participants' home (if they live within a 75-mile radius of NCCH), or (3) virtually via video conferencing if an in-person visit is not feasible. If participants request to participate in a home-based study visit then the intervention facilitator will travel with another member of the study team.

Participants will be provided a five-week interval to complete study visit assessments. The assessment window begins immediately after completing the face-to-face meeting with the intervention facilitator until five weeks after the study visit or immediately before participating in their next study visit – whichever time point occurs first. Participants can complete study assessments via an online Qualtrics link, via hard copy, or via telephone.

The intervention facilitator will be the PI or a trained licensed clinical social worker with experience providing clinical care to oncology and palliative medicine patient populations. The intervention facilitator will conduct the study visit in accordance with the study manual (see Appendix D for Intervention Facilitator manual) and patient education materials (see Appendix E for patient education materials) and will prepare a written memo after each study visit with participant dyads. The study visits with the intervention facilitator will be audio-recorded and professionally transcribed to aid with treatment fidelity monitoring and qualitative analyses.

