Risk of emotional distress. All eligible patients for this study will have a diagnosis of metastatic breast cancer – an incurable illness frequently associated with intense emotional, physical and spiritual distress. All eligible co-parents for this study will have a loved one who has metastatic breast cancer. Both patients and co-parents may be at higher risk for temporary additional emotional discomfort or distress due to this study. Questions about quality of life, prognosis, parenting concerns, and EOL planning may be temporarily uncomfortable or distressing for some participants. We expect the risks of discomfort or distress to be moderate relative to the overall distress that the patients and their families experience due to their terminal illness. We have successfully conducted studies evaluating psychological distress, treatment decision-making, prognostic understanding, and supportive care needs with the patient and co-parent population described in the eligibility section above. Prior participants with a wide range of educational backgrounds, illness severity, and psychological adjustment have described our study practices as appropriate and acceptable. In addition, all intervention materials have previously undergone extensive review by a panel of patient, caregiver, and healthcare provider stakeholders (see LCCC1719 for details of this process) to enhance the relevance, acceptability, and emotional and cultural sensitivity of study materials.

In addition, the PI will continuously supervise the RA and intervention facilitator and conduct a 2-day training focused on how to recognize and address psychological distress or other concerns among participants that may occur during the course of the study. The training will consist of role plays and case examples, didactic and training manual materials, and review of the literature and available clinical resources. Training with the RA and intervention facilitator will be repeated as necessary throughout the study.

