## 7.0 STATISTICAL CONSIDERATIONS

### 7.1 Study Design

This study is the second phase of a three-phase project to develop and pilot test a psychosocial intervention tailored to parents with advanced cancer and their co-parents.

The first phase was an observational study with patient, caregiver, and healthcare provider stakeholders to obtain feedback on the intervention (see approved protocol LCCC1719). The second phase (currently proposed) is a pilot single-arm trial to assess the acceptability and feasibility of the newly developed intervention. The third phase will be a RCT to test the preliminary efficacy of the intervention versus usual care.

In this single-center, single-arm interventional pilot study, we will recruit ten patients and their co-parent (n=20) to participate as dyads in a novel psychosocial intervention for parents with advanced cancer and their co-parents. This is a non-randomized study due to the need to preliminarily test the acceptability and feasibility of study procedures. Dyads will participate in two to three (third visit is optional) structured psychotherapeutic counseling visits addressing parenting concerns facilitated by the PI or a licensed clinical social worker (supervised by the PI). Participants will also receive psychoeducational materials targeted to their parenting concerns. Participant dyads will complete study assessments at baseline and after every study visit. At the end of the study they will participate in semi-structured interviews assessing their experiences with the study. Study investigators will then refine the study in preparation for a pilot RCT to test the efficacy of the intervention. The primary hypothesis being tested is that a psychosocial intervention to reduce psychological distress and improve end-of-life preparation for mothers with metastatic breast cancer and their co-parents can be acceptable to the target patient population.

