### **Evaluate feasibility of the intervention**

**To evaluate feasibility of intervention procedures**, we will report the percentage of patient-co-parent dyads who enroll and complete the intervention as well as descriptive statistics on the demographic characteristics of patients and co-parents who enter, remain in, and drop out of the study. We will use descriptive statistics and qualitative analyses of post-intervention semi-structured interview data to explore barriers and facilitators to enrollment and retention, including reasons for enrollment, non-participation (e.g. fears of unintended outcomes, competing demands, etc.), ineligibility, or withdrawal and use this information to refine the intervention.

We will evaluate study procedure feasibility including the number of patients screened each month, the number of contacts necessary to enroll participants and schedule follow-up appointments, the duration of each study visit, the proportion of completed study measures at each visit, and the time it takes to complete these measures. Although adverse events are unlikely, we will examine the procedures for adverse event reporting and the study teams' response to such events.

To assess fidelity of the intervention—an aspect of feasibility critical to future implementation needs for the RCT—the PI will individually review audiotapes of each study visit to ascertain adherence to the protocol and underlying theory, and will rate each session according to an intervention checklist. The PI will provide re-training and feedback to the intervention facilitator if any problems in conducting sessions or adhering to protocol arise.

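### The PI may both facilitate a dyad's sessions and conduct that dyad's feedback interviews; a short separation rule with a documented fallback would reduce an avoidable exposure in one of the two primary acceptability sources

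*Combined protocol and SAP*

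**What the plan says.** **Who delivers the sessions.** Section 4.3 (Study visits) states: "The intervention facilitator will be the PI or a trained licensed clinical social worker with experience providing clinical care". Section 7.1 repeats the choice, describing "structured psychotherapeutic counseling visits addressing parenting concerns facilitated by the PI or a licensed clinical social worker (supervised by the PI".

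**Who takes the feedback.** Section 4.3 (Post-intervention study interview) states that "participants will individually participate in a semi-structured interview with a member of the study team (PI or RA) to obtain feedback on the intervention". Each partner is interviewed separately.

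**What the interview is for.** Section 2.1 bases the primary acceptability objective on two sources, satisfaction ratings and interviews. Section 7.3 says that the interview feedback will be used to refine the intervention before the RCT. It has the RA and the PI code the transcripts, and it plans to bring the rating and interview findings together after separate analysis.

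**Text that treats the PI and the facilitator as two people.** Section 4.3 (Study team assessments) says that "the PI and intervention facilitator will independently complete an intervention fidelity checklist". Section 4.4 says that "the PI will continuously supervise the RA and intervention facilitator". Section 7.3 says: "The PI will provide re-training and feedback to the intervention facilitator if any problems in conducting sessions or adhering to protocol arise". None of these bars the PI from facilitating or from interviewing.

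**The concern.** The PI is the only role named both as facilitator and as interviewer, and the protocol body has no rule keeping the two apart within a dyad. A participant could therefore be asked what was wrong with the sessions by the person who ran them.

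Several interview topics in Section 7.3, such as tone, phrasing and emotional sensitivity, invite comment on delivery. That is hard to criticise to the person who delivered it. The relationship may also continue: Section 4.3 offers telephone access to the facilitator after the visits and has the facilitator make the bereavement call. It also foresees that some patients may be under the PI's own care.

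What is at stake is candour in a primary data source. The study has no control arm and no numeric acceptability threshold, so its conclusion depends on what participants are willing to say. Member checking and an audit trail work on what was said; they cannot recover criticism that was never voiced. The planned triangulation is between patients and co-parents, who attended the same sessions with the same facilitator and could be affected alike.

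**Working it through.** The plan states no figure for this point, so there is none to reproduce. The check sets the role assignments side by side and then bounds the exposure.

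**1. Roles**

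| Role | May facilitate (4.3, 7.1) | May hold the post-intervention interview (4.3) |
|---|---|---|
| PI | yes | yes |
| Social worker | yes | not named |
| RA | not named | yes |

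The overlap can arise only through the PI, and only when the PI facilitated a dyad and also interviewed one of its members.

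**2. Maximum number of interviews.** Section 7.2 gives 10 dyads, so 10 × 2 = 20. This is a ceiling: Section 4.5 foresees death, impairment, withdrawal and loss to follow-up, and under 4.3 those who withdraw remain eligible for the interview but need not take part.

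**3. Exposure.** Let k be the number of dyads in which the PI facilitated any session. Defining k by any session covers a dyad seen by both facilitators, since no text fixes one facilitator per dyad. Exposed interviews ≤ 2k. As a share of the full 20:

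- k = 0: 0
- k = 1: 2/20 = 10%
- k = 5: 10/20 = 50%
- k = 10: 20/20 = 100%

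The documents give neither k nor the number of interviews the PI will hold. An interview held by the RA, or in a dyad seen only by the social worker, is not exposed. Under the rule below, exposure is limited to documented fallback cases.

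**4. The less exposed source.** Study visits are split into "1) a face-to-face meeting with the intervention facilitator, and (2) data collection with the research assistant". Forms may be completed online, on paper or by telephone, and each partner completes them separately. Satisfaction is rated after each of two or three visits, so full completion gives 20 × 2 = 40 to 20 × 3 = 60 rating forms.

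**5. Time moved to the RA.** Section 4.3 gives 30 to 45 minutes per interview. Per PI-facilitated dyad: 2 × 30 = 60 to 2 × 45 = 90 minutes. At most: 20 × 30 = 600 minutes = 10 hours, to 20 × 45 = 900 minutes = 15 hours.

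No rate of withheld criticism is assumed, because the documents offer nothing from which to derive one.

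**The case against.** **No contradiction is shown.** This stands. A reader might infer that the PI will interview the people the PI counselled. The documents do not say so, and the passages on the fidelity checklist, supervision and re-training read as if the facilitator were usually someone else. They set no rule, however, and 4.3 describes the PI as a real facilitator option.

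**A rule may exist elsewhere.** Appendices D and F are listed but were not available. The absence of a rule is shown only for the protocol body.

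**Other evidence limits the damage.** This stands in part. Section 7.3 brings ratings and interviews together, so a marked discrepancy could show. It also says "we will report the percentage of patient-co-parent dyads who enroll and complete the intervention", and those figures do not depend on who interviews. Study visits are recorded and transcribed, and the materials had prior stakeholder review. None of this reliably recovers a criticism that a participant chose not to make.

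**Separation gives only partial independence.** This also stands. A reader might infer that RA interviewing would make the interview source independent of the PI. It would not: the PI supervises the RA and still co-codes the transcripts, and the RA already knows the dyad from data collection at the visits.

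**An RA-only rule could cost interviews.** With no backup interviewer, an RA absence could lose a seriously ill participant's interview. This is a fair objection to an absolute rule, and the reason the fix has a fallback.

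**Conclusion.** The point holds as a cheap improvement to a design choice, at the level of something to consider, with medium confidence. As written, the protocol allows participants to give feedback to the person who counselled them, in one of the two sources for the primary objective. Exposure is at most 2k of at most 20 interviews, with k unstated and possibly zero.

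A reader might go further and conclude that the acceptability findings will be biased or cannot be relied on. The documents do not support that. The overlap may never occur, the size of any effect cannot be estimated, and the ratings and their planned convergence with the interviews mitigate it in part.

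The conclusion rests on two assumptions: that the unavailable appendices contain no separation rule, and that some participants speak less freely to their own facilitator. The second is plausible but is not quantified in the documents.

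**What to change.** **Section 4.3, Post-intervention study interview.** Keep the PI and the RA as the named interviewers and add wording to this effect: *Anyone who facilitated any session with a dyad will not conduct that dyad's post-intervention interviews; where the PI facilitated, the RA will interview. If the RA is unavailable within the seven-week window, the PI may interview, and this will be documented.* The window is the one already in Section 4.2. If Appendix F already has such a rule, citing it in 4.3 is enough.

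**Section 7.3, acceptability.** Add that who facilitated and who interviewed each dyad will be reported alongside the acceptability results. This helps even for interviews already held.

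The case for extending the rule to the optional 6-month interview is weak, because 7.3 names only the post-intervention interviews as an acceptability source.

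**Cost.** Two short additions to the text and no new role: the RA is already a named interviewer and, under Section 4.4, is trained to recognise and address distress. At most 10 to 15 hours of interviewing move to the RA; the documents give no figure for RA capacity. Scheduling is less flexible for PI-facilitated dyads, which the fallback eases. Dyads seen only by the social worker are unaffected. The PI's supervision of the RA and share in coding would remain.
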